
	continuous measure based on total percent of methylation for each NR3C1 and HSD11B2 promoter region as well as for each individual CpG site.	
Gut Microbiome	
Infant fecal samples will be collected by a bedside nurse in the NICU at baseline, 34 weeks PMA, NICU discharge. For the 2 months CA sample, parents will receive a fecal collection kit with written instructions to collect and send samples to our lab via USPS postal services.
 
Fecal samples from each infant will be collected using sterile, disposable spatulas during diaper changes and then placed into a sterile specimen container with microbial DNA stabilizer solution for 60 days at room temperature. The samples collected will be transported to a laboratory at the Loyola University Chicago Center for Translational Research and Education (Maywood, IL). All samples will be stored at room temperature. Monthly, the buccal swab samples will be securely transported in a biospecimen transfer container (Saf T Pak, Austell, GA) via car to Rush University Medical Center Genomics and Microbiome Core Facility (Chicago, IL) for processing and analyses. Genomic DNA will be extracted from fecal material using a Maxwell RSC48 autM-MILKted extraction device (Promega) and employing a Maxwell RSC Fecal Microbiome DNA kit, as described previously.⁶⁴ Samples will be subject to physical shearing (i.e., bead-beating) using a TissueLyser II device (Qiagen) prior to extraction. Genomic DNA will be prepared for sequencing using a two-stage amplicon sequencing workflow⁶⁵ and employing primers 515F-modified and 806r-modified.⁶⁶ Sequencing will be performed a MiniSeq sequencer (Illumina)⁶⁴ with paired-end 2x154 base sequencing. Basic processing of sequence data, including merging of forward and reverse reads, quality and primer trimming, chimera removal, and selection and annotation of amplicon sequence variants (ASVs) will be performed.⁶⁴ Alpha diversity indices (e.g., Shannon index) will be calculated on rarefied datasets⁶⁷ in R using the vegan library package.⁶⁸ Pairwise comparisons of alpha diversity indices will be performed using the non-parametric Mann–Whitney test. Beta diversity analyses will be performed on pairwise Bray–Curtis indices calculated in R using the metaMDSdist function in the vegan library v2.5-6. The dissimilarity indices will be modelled and tested for significance with the sample covariates using PERMANOVA.⁶⁹ Differential abundance analyses of individual taxa between groups will be performed using the software package DESeq2, generating an FDR q-value.⁷⁰ DESeq2 has been shown to be appropriate for differential abundance comparisons in studies with small sample size groups (< 20) or unbalanced design.⁷¹ To identify taxa that most strongly explain between-group differences, a Linear discriminant analysis Effect Size (LEfSe) analysis will performed.⁷¹
	T0, T1, T3, T4 Fecal samples
Charges and costs of care	Healthcare use and associated charges and costs of the NICU hospitalization and 2 months CA care will be extracted from LUMC's electronic health and billing records. For infants receiving care outside LUMC 2 months CA, we will ask the parents about the extent and types of healthcare received outside LUMC. We will evaluate healthcare use, costs, and charges between the M-MILK and control groups. We will also describe the extent and types of healthcare use 2 months CA for infants receiving care outside LUMC at discharge. In the R01 trial, we will use activity-based costing approach to calculate the time and resources costs of delivering the M-MILK intervention by nurses and parents (which may not be fully reflected in the health system billing records), and query NICU hospitalization and 2 months CA healthcare use, charges, and costs to calculate total benefits and costs of M-MILK Intervention vs. control group.	T3 & T4
M-MILK Acceptability Questionnaire	The M-MILK Acceptability Questionnaire will be completed by parents at discharge. The nurses will complete the M-MILK Acceptability Questionnaire at the end of the entire study.	T3 M-MILK Acceptability Questionnaire

Note. EPIC = electronic medical record; GA = gestational age; PMA = postmenstrual age; CA = corrected age; Ongoing = throughout hospitalization from enrollment to discharge; T0 = baseline; T1 = 34 weeks PMA; T2 = oral feeding initiation; T3 = discharge; T4 = 2 months CA

ii. Procedures

Figure 2. After informed consent is obtained, infants will be randomized into: Group 1 (M-MILK) and Group 2 (attention control). All data collection will be conducted in the same manner and at the planned time points for both groups. For all infants, we will collect infant characteristics, NISS, and family NICU activities daily ongoing from EPIC and self-report. All parents will receive an automatic daily text in the morning with a link to report their daily activities with infants when they come to the NICU. All parents are signing up for daily texts for up to 20 weeks to complete daily activities report every day during their participation. All parents will also receive a weekly phone call from a research nurse from enrollment until discharge. M-MILK is primarily implemented by nurses or parents. **At baseline (T0)**, we will conduct the EPDS assessment, and collect parent characteristics,

buccal swab and fecal samples. For infants in the M-MILK group, the clinical team will place an order in EPIC for M-MILK to be provided starting on day 3 of life according to the M-MILK protocol. We will also schedule an in-person 30-minute M-MILK training session with parents in the M-MILK group, within 1 week of enrollment, provided by a research nurse. Parents in the M-MILK group are encouraged and supported to provide M-MILK when appropriate with the nurse's supervision. **At 34 weeks PMA (T1)**, we will collect PBQ, buccal swab and fecal samples. **At oral feeding initiation (T2)**, we will collect the EFS, and NCAST-Feeding video recording. Day of initiation of oral feeding is defined as the first of at least two consecutive days when the infant is able to orally consume $\geq 10\%$ of their prescribed feedings. Infants will be fed by nurses, speech therapist, or PI. We will implement the same feeding protocol, e.g., side-lying and swaddling during feeding. **During the week of planned discharge (T3)**, we will conduct EPDS, PSS: NICU, PDR, PBQ, Pumping and Breastfeeding, NMI, NAPI, and EFS assessments. We will collect NCAST-Feeding video recording, buccal swab and fecal samples. For the NCAST-Feeding video recording, both parents and infants will be recorded. Parents will also complete the M-MILK Acceptability Questionnaire at T3. For EFS and NAPI assessments, we will video record the assessments, when possible, to obtain videos for inter-rater reliability. **At 2 months CA (T4)**, we will send parents the fecal and buccal sample collection kits via USPS mail service. We will also conduct a phone/Zoom interview to complete the EPDS, PBQ, ASQ-3, and NeoEAT assessments. During the phone/Zoom interview, we will also provide parents instructions on how to collect buccal and fecal samples and securely send them back to us.

VIII. Safety Monitoring Plan

a. Potential Risk

IRB oversight and approval will be based on 45CFR 46 HHS criteria. We anticipate our study will be determined to be no more than "minimal risk". The M-MILK intervention's safety has been demonstrated in infants as young as 22 weeks GA. According to the M-MILK protocol, nurses or parents will carefully observe infants' cues and responses during the M-MILK intervention and stop the administration if infants do not engage or exhibit any signs of distress. Thus, there is minimal risk associated with this protocol. Every effort will be made to minimize the risks. There may be risks associated with administration of M-MILK and collecting buccal swab samples including gagging and minor discomfort. Of note, these risks are no more expected risks to infants than what they might experience during a typical day, routine oral care, or feeding. Nurses will document infants' responses or any unexpected and serious adverse events to M-MILK intervention in the M-MILK Documentation paper sheet. A research nurse will review the documentation and report to PI if there are any unexpected and serious adverse events. For the NAPI assessment, we will perform maneuvers such as partially removing swaddle blanket, gentle stretching/bending of arms and legs, gently picking up, and stimulating vision and hearing with soft rattle sounds and talking voices. These maneuvers may pose minimal risks such as feeling cold, and mild discomfort due to stretching/bending/picking up, or noises. Of note, these risks are no more expected risks to infants than what they might experience during a typical day, routine care, or physical exam. Additionally, this research also carries a minimal risk of loss of data confidentiality/security. We also recognize that there are unique risks related to loss of confidentiality regarding a participant's epigenetic and microbiome data; however, we consider this risk to be rare.

b. Adequacy of Protection Against Risks

i. Informed Consent and Assent

The potential risks will be presented to the parents prior to enrollment. If parents are interested in having their preterm infants participate in the study, written informed consent will be obtained. Alternatively, the potential preterm infant will receive standard care if the parents choose to not enroll in the study. Premature infants, by virtue of their age cannot give consent or assent and therefore will not give assent or participate in the informed consent process.

ii. Protections Against Risk

1. Risks Related to Study Procedure

During the study, if an infant becomes clinically unstable and/or develops new diagnosis, and no longer meet the inclusion criteria, we will remove the infant from the research protocol. The M-MILK intervention's safety has been demonstrated in infants as young as 22 weeks GA. According to the M-MILK protocol, nurses or parents will carefully observe infants' cues and responses during the M-MILK intervention and stop the administration if infants do not engage or exhibit any signs of distress. When collecting the buccal swab samples and administering NAPI, we will make every effort to be as gentle as possible and omit any item(s) that may be causing discomfort to infants. If parents report a score of 12 or above on the EPDS, we will make referrals to the NICU Social Worker. If parents report "yes, quite often" or "sometimes" to the question "the thought of harming myself has occurred to me" on the EPDS, we will refer the parent to the local Emergency Department immediately. For the PBQ, parents scoring ≥ 26 , (indicating risk of general bonding disorders) or ≥ 40 (indicating risk of severe bonding disturbances) should seek medical attention. For the PBQ, parents scoring "rarely", "sometimes", "quite often", "very often", or "always" for item 18 "I have done harmful things to my baby" or item 24 "I feel like hurting my baby" indicates risk of child abuse. In this case, it is our responsibility to report it to the state's child protective agency. If the infant is in immediate danger, the research staff will be instructed to inform the parents of their immediate concerns for the infant's safety, report the incident using a cellular phone, and call 911 until appropriate officials arrive. The PI will be informed of the family's condition and always be available by phone or in person for consultation and instruction. As part of the training of our research team, the team will review content related to reporting of child neglect and abuse.

2. Risks related to Data Confidentiality

Risks associated with loss of electronic data confidentiality/security will be mitigated through the utilization of secure electronic database (REDCap) and research network drive process to ensure that only authorized research personnel have access to the research data. The original signed informed consent documents will be kept in a locked cabinet at LUC CTRE. All infants will be assigned a study ID number. All of the data will be identified only by a study ID number. All discussions of specific research participants in our research team meetings will use this number rather than names. Electronic data will be encrypted with a password known and viewed only to the research staff. The password will be changed every six months.

The M-MILK Documentation paper sheets will have the infant's name on it and is available at the infant's bedside for nurses to document M-MILK. The completed sheets will be collected daily by a NICU charge nurse and stored in a locked cabinet on the unit. A research team member will pick up the completed sheets daily, and stored them in a locked cabinet in at LUC CTRE (Maywood, IL) for data entry. Upon completion of data entry into REDCap, the completed sheets will be shredded immediately.

Buccal swab and fecal samples will be labeled only with study ID numbers and collection date, and stored in a locked cabinet in a locked laboratory at LUC CTRE (Maywood, IL). We will securely transport buccal swab and fecal samples to Rush (Chicago, IL) using biosafety transfer containers and via car.

Video recordings will be downloaded and stored on a secure research network drive, hosted by LUC. Infant's and parent's face will be visible in the videos as we need to observe their interactions and infant's feeding skills. However, we will not include any identifiers such as name or date in the videos. The video files will be labeled only with study ID numbers and recorded date.

De-identifiable data will be shared with University of Illinois at Chicago Research Informatics Core. All data; e.g., raw sequence data, processed data and sample mapping; will be transmitted between systems via encrypted transport protocols, i.e. HTTPS or SFTP. All desktop and laptop computers are protected by strong password authentication with whole disk encryption enabled. Remote servers are protected by network firewalls, intrusion detection software, and either bastions or two factor authentication for any remote logins. Any passwords on the remote systems are subject to strong password requirements, i.e., minimum password length, combinations of different character types (capital letters, lowercase letters, numbers, special characters), and are not typical English words.

Biospecimens are materials that come from infants that may include blood, tissue, urine, bone marrow, saliva, cells, etc. In this study, we will collect cheek tissue and stool. Most biospecimens contain DNA. We will not use biospecimens collected as a part of this study for whole genome sequencing. However, we will use biospecimens collected as a part of this study to sequence a short portion of the genes of interest that starts gene transcription found at the beginning of the genes. The de-identified sequence data will be submitted to online government data repositories per National Institute of Health requirements. All the sources of the sample are de-identified and infants' individual identity will not be revealed.

De-identified data, photos and/or selected brief segments of videos from this study may be shared with others for research/educational purposes in reports, scientific papers, research/educational meetings, and/or research/educational websites. De-identified data, photos and/or selected brief segments of videos from this study may also be shared on research/educational social media platforms. We will remove or code any personal identifiable information that could identify participants before data are shared with other researchers to ensure that no one will be able to identify participants from the information we share. De-identified data, the photos and/or selected brief segments of videos will be stored indefinitely. Informed consents and video recordings will be securely shredded/deleted after all related data are published or up to 5 years. Buccal swab and fecal samples will be stored and securely destroyed after all related data are published or up to 5 years.

If any data are lost or stolen, the PI will immediately notify the LUC Information Services, at [contact] and will notify the LUC IRB of any unusual occurrence.

The results of this research study may be published in a journal for the purpose of advancing medical knowledge. You will not be identified by name or by any other identifying information in any publication or report about this research. When we prepare our reports or publications, we will summarize the results of the research in a manner that will not reveal infants' identity. In addition, no names will be used in any report of this study. We may want to use photos and/or brief segments of the videos to illustrate infants' feeding skills and behaviors in reports, scientific papers, or educational meetings. We will obtain parents' written permission for use of evaluation photos and videos for educational purposes.

3. Report of child neglect and abuse to the appropriate authority

Researchers and professionals who work with families with children under the age of 18 are responsible for the welfare of children. For the PBQ, parents scoring "rarely", "sometimes", "quite often", "very often", or "always" for item 18 "I have done harmful things to my baby" or item 24 "I feel like hurting my baby" indicates risk of child abuse. If the research team suspects an infant has been physically or emotionally abused or neglected, following the guidelines set by the state during study evaluations, it is our responsibility to report it to the state's child protective agency. If the infant is in immediate danger, the research staff will be instructed to inform the parents of their immediate concerns for the infant's safety, report the incident using a cellular phone, and call 911 until appropriate officials arrive. The PI will be informed of the family's condition and always be available by phone or in person for consultation and instruction. As part of the training of our research team, the team will review content related to reporting of child neglect and abuse.

iii. Vulnerable Subjects

This research study is intended to evaluate an intervention for a specific group of preterm infants, those born between 22 to 33 weeks GA. It is essential that infants under one year of age are included. Older children are excluded because the study is evaluating preterm infants only. Our research team has expertise for working with preterm infants. For example, [name] has more than 12 years of experience working with preterm infants and their families. [name] has more than 10 years of clinical experience and 40 years of research experience conducting numerous research projects, including H-HOPE intervention with neonates and their mothers. The infants will be cared for in the NICU as part of their hospitalization. The team will follow the U.S. Department of Health and Human Services regulatory requirements for parental permission and child assent for research involving children. Preterm infants, by virtue of their age cannot give consent or assent and therefore will not give assent or participate in the informed consent process.

IX. Data Management and Analysis Plan

Strict confidentiality of data files will be maintained. Data management will be facilitated using REDCap. SAS (v 9.4) will be used for all statistical procedures and analyses. Levels of missingness, variable distributions, and outliers will be examined throughout data collection for quality assurance as well as prior to statistical modeling. We will calculate descriptive statistics for all variables of interest to describe the variability of study variables, and conduct sample size estimation for the planned R01 application. Comparisons will be made using an intent-to-treat approach with participants analyzed in the groups to which they were randomized. Feasibility will be assessed with respect to enrollment, adherence, acceptability, and safety. We will calculate the percentage of infants who (1) were eligible, approached, consented, enrolled, and randomized over the recruitment period, (2) were retained for the duration of the study, (3) completed all inpatient data collection, and (4) completed post-discharge follow-ups. To determine the adherence of M-MILK, we will calculate the daily numbers of completed M-MILK and the daily numbers of expected M-MILK implementation (numbers of hands-on care episodes before full gavage feedings) to obtain the daily percentage of M-MILK completion. We will summarize findings from M-MILK Acceptability Questionnaire by nurses and parents. We will also summarize findings from M-MILK EPIC charting regarding infant's responses and any adverse events to monitor for the safety of M-MILK.

X. Study Timeline

Table 2. The proposed pilot study will require 1 year to complete. During the first 3 months, we will hire and train the team members. We anticipate enrolling 2 infants per month for 9 months. An additional 3 months will be required to complete the intervention and collect study data. Data entry and analyses will be ongoing. We will spend 6 months to complete data analyses. An additional 6 months will be needed to prepare the final report and disseminations.

Table 2. Study Timeline

Activity/Month	Month 1-3	Month 3-12	Month 12-15	Month 15-21	Month 21-27
Preparation & Staff Training	X				
Recruitment & Enrollment		X			
Data Collection		X	X		
Data Entry & Analyses		X	X	X	
Final Reports & Dissemination				X	X

XIII. Literature Cited

1. Barfield WD. Public Health Implications of Very Preterm Birth. *Clin Perinatol*. Sep 2018;45(3):565-577.

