The aims of this pilot study are to (1) determine the feasibility and acceptability of the M-MILK intervention by nurses and parents, (2) determine the feasibility of recruitment and retention, (3) obtain variability data for sample size estimation, and (4) evaluate the charges and costs of the NICU hospitalization and 2 months CA care between the M-MILK and control groups. M-MILK will be considered feasible if M-MILK is implemented by nurses or parents after every hands-on care and during the beginning of a full gavage feeding at least 90% of the time. The M-MILK acceptability by nurses and parents will be determined via M-MILK Acceptability Questionnaire. Recruitment and retention will be considered feasible if at least 50% of infants approached for participation enrolled, 90% of infants completed all inpatient data collection, and at least 50% of infants completed post-discharge follow-ups.

V. Administrative Organization

Participants will be enrolled in the Neonatal Intensive Care Unit (NICU) at Loyola University Medical Center (LUMC) (Maywood, IL). The inpatient components of the study protocol will be conducted in the NICU at LUMC. The post-discharge follow-up components of the study protocol will be conducted via phone/zoom interview. Data storage and management will be carried out via REDCap (version 10.4.0, Vanderbilt University) and a secured research network drive, hosted by the Loyola University Chicago (Maywood, IL).

Upon sample collection, buccal swab and fecal samples will be labeled only with study ID numbers and collection date, and stored in a locked cabinet in a locked laboratory at Loyola University Chicago (LUC) Center for Translational Research and Education (CTRE). All samples will be stored at room temperature. Quarterly, the buccal swab samples and fecal samples will be securely transported in a biospecimen transfer container (Saf T Pak, Austell, GA) via car to Rush University Medical Center Genomics and Microbiome Core Facility (Rush) (Chicago, IL) for processing and analyses. A Service Agreement between LUC and Rush will be submitted through LUC Research Portal.

VI. Study Design

a. Design

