DNA methylation of NR3C1 & HSD11B2	
We will evaluate DNA methylation in buccal cell DNA collected at baseline, 34 weeks PMA, NICU discharge, and 2 months CA, as an index of early life toxic stress. A trained research team member will be collecting, transporting, and storing the samples. We will collect two buccal swab samples from each infant at each visit using Isohelix DNA Buccal Swabs (Boca Scientific, Westwood, MA) before feeding to avoid contamination. The buccal swab samples will immediately be placed in a storage tube with a DNA stabilizer Dri-Capsule (Boca Scientific, Westwood, MA). The samples collected will then be transported to a laboratory at the Loyola University Chicago Center for Translational Research and Education (Maywood, IL). All samples will be stored at room temperature. Quarterly, the buccal swab samples will be securely transported in a biospecimen transfer container (Saf T Pak, Austell, GA) via car to Rush University Medical Center Genomics and Microbiome Core Facility (Chicago, IL) for processing and analyses. DNA will be extracted from buccal swab samples using the Maxwell® RSC Buccal Swab DNA Kit (Promega, Madison, WI) implemented on an automated Promega RSC device. The DNAm status for both the NR3C1 exon 1F and HSD11B2 promoter regions will be assessed using quantitative bisulfite amplicon sequencing using an Illumina MiSeq sequencer. Preparation of the bisulfite-converted DNA for sequencing will be accomplished with primers for NR3C1 and for HSD11B2, as described,¹¹ employing a two-stage polymerase chain reaction protocol.⁶⁰ Using the Illumina MiSeq sequencer, we will be able to sequence the entire targeted region, including the 13 NR3C1 CpG sites in the 1F region and the 4 HSD11B2 CpG sites. These sites are associated with neuroendocrine system regulation, including the HPA axis, and cortisol reactivity in rodent and human studies.^{21,61-63} Bisulfite conversion controls will be included with each sequencing run and will also be assessed for non-CpG 'C's. Samples with conversion rates below 93% will be re-processed. Libraries will be prepared in technical triplicate from each bisulfite converted DNA template, and if the replicates differ by $> 10\%$, the sample analysis will be repeated. Unmethylated CpG sites will be converted to UpG (TpG upon PCR amplification) by bisulfite treatment. The percent methylation at any nucleotide coordinate will be determined by the ratio of C residues (derived from 5-methylcytosine) to C+T residues (derived from 5-methylcytosine plus cytosine, respectively) at any position within the NR3C1 and HSD11B2 genomic DNA sequence. In addition, the methylation status of each read will be assessed individually by counting the number of methylated CpG sites observed within that read and summed to assess average methylation status in each amplicon. The percent DNAm at the NR3C1 and HSD11B2 promoters and at each CpG site will be quantified using CLC genomics workbench (Qiagen) software package. DNAm data will be analyzed as a
	T0, T1, T3, T4 Buccal samples

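### Fecal transport is quarterly in Section V but apparently monthly in Table 1; if the quarterly rule is followed, about a third of stool samples would outlast the stated 60-day stabilizer period

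*Combined protocol and SAP*

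**What the plan says.** Three sentences in the combined protocol and SAP set the transport interval to the core laboratory.

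- Section V (Administrative Organization) covers both specimen types: "Quarterly, the buccal swab samples and fecal samples will be securely transported in a biospecimen transfer container". The sentence before it reads "All samples will be stored at room temperature".
- Section VII, Table 1, DNA methylation row, covers buccal swabs only: "Quarterly, the buccal swab samples will be securely transported in a biospecimen transfer container".
- Section VII, Table 1, Gut Microbiome row, describes the fecal procedure, yet its transport sentence reads "Monthly, the buccal swab samples will be securely transported in a biospecimen transfer container".

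The Gut Microbiome row also gives the only storage duration for stool. Samples are "placed into a sterile specimen container with microbial DNA stabilizer solution for 60 days at room temperature".

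On collection times, the same row says "Infant fecal samples will be collected by a bedside nurse in the NICU at baseline, 34 weeks PMA, NICU discharge". A fourth sample, at 2 months corrected age (T4), is collected by parents and posted to the laboratory. Section V puts the collection date on every sample label. No section sets a maximum time from collection to extraction.

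**The concern.** A quarter is about 90 days, and the only duration given for stabilized stool at room temperature is 60 days. The one transport sentence that names fecal samples therefore overruns the plan's own figure. The one sentence with a shorter interval names the wrong specimen. Staff who work from Section V would hold some stool samples past 60 days and have nothing to tell them so.

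Aim 3 of the pilot is to obtain variability data for sizing the planned R01 trial, and the gut microbiome is measured at four time points. If storage beyond the stabilizer period affects the sequence data, storage age becomes an extra source of variation in the diversity and abundance measures. With 6 infants per group, a few affected samples could matter. The plan includes no record of storage age, no adjustment for it, and no rule for samples held too long.

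**Working it through.** The documents state no share of over-age samples, so there is no figure of the plan's to reproduce. The check first compares the sentences and then works out what each schedule implies.

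**Sentences side by side**

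| Place | Specimen named | Interval |
|---|---|---|
| Section V | buccal and fecal | quarterly |
| Table 1, DNA methylation row | buccal | quarterly |
| Table 1, Gut Microbiome row | buccal (within the fecal procedure) | monthly |

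Read literally, buccal swabs have two schedules and stool has only the quarterly one. The monthly sentence, however, stands between fecal storage and fecal DNA extraction. The part quoted above differs from the methylation-row sentence only in its first word. The likeliest explanation is that the sentence was copied, its interval was changed for stool, and the specimen name was left as it was.

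**Inputs**

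- Transport interval L: 90 to 92 days for a quarter (12 weeks = 84 days as a low variant); 28 to 31 days for a month.
- Stabilizer period: 60 days (Table 1, Gut Microbiome row).
- Infants: 12 (Section VI, Sample). The opening summary says 20; the share does not depend on this number.
- Fecal samples per infant: 4 (three inpatient, one at T4).
- Assumption, not in the documents: collection dates are spread evenly over each interval, and storage ends on the day of transport.

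**Share held longer than 60 days** = max(0, (L − 60)/L)

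- L = 84: 24/84 = 28.6%
- L = 90: 30/90 = 33.3%
- L = 91: 31/91 = 34.1%
- L = 92: 32/92 = 34.8%
- L = 28 to 31: 0%, with a longest hold of 31 days

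**Counts under quarterly transport (L = 90 to 92)**

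- Full retention: 12 × 4 = 48 samples. 48 × 0.333 = 16.0; 48 × 0.348 = 16.7.
- Half of the T4 samples returned (the follow-up threshold in Section IV): 12 × 3 + 6 = 42 samples. 42 × 0.333 = 14.0; 42 × 0.348 = 14.6.

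**Effect of a mailing or processing lag of d days**, with L = 91.25 (one quarter of a year): (91.25 + d − 60)/91.25

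- d = 0: 31.25/91.25 = 34.2%
- d = 3: 34.25/91.25 = 37.5%
- d = 7: 38.25/91.25 = 41.9%
- d = 14: 45.25/91.25 = 49.6%

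These lags are illustrative and are applied to every sample; the mailing part concerns T4 only. Under monthly transport, a 14-day lag gives a longest age of 31 + 14 = 45 days, still within 60.

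**The case against.** The strongest reply is that the detailed procedure already holds a workable schedule. If the Gut Microbiome row means fecal samples where it says buccal swabs, stool travels monthly and nothing passes 60 days. The fault is then a copying slip plus an administrative summary that disagrees with the methods table. That reading is the more plausible one. A reader might infer from Section V alone that a third of the samples will overrun, or that the plan intends no adequate schedule for stool. The documents do not support either as an unconditional statement.

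Further points carry weight. The 60 days is never called a limit; a stability period is its natural reading, but it is a reading. Even collection is an assumption, and with 12 infants the actual share could be quite different. Forty-eight samples requires full retention, while Section VI anticipates 40% attrition. A reader might also infer that microbiome variance will be inflated or the arm comparison biased. Nothing in the documents says what happens to these samples after 60 days, or by how much. Arms are randomized, and the Procedures section has data collected in the same way and at the same time points in both groups. Finally, no feasibility threshold in Section IV depends on microbiome results.

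What the reply does not remove is the conflict itself. The only sentence that names fecal transport says quarterly, the sentence that would correct it names another specimen, and no maximum time to extraction is set.

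**Conclusion.** The plan contradicts itself on fecal transport and should be corrected before samples are collected. The size is conditional. If Section V is followed, roughly a third of fecal samples (33% to 35%) would be held beyond 60 days, and more with any lag. If monthly transport applies to stool, none would. The first figure rests on even collection over a 90 to 92-day cycle and on taking the 60 days as the stabilizer's stated period.

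The consequence is a preventable risk of storage-related variation in the microbiome part of aim 3. Its size and direction cannot be derived from the documents. The point does not touch the pilot's adherence, recruitment or retention criteria. It merits correction because it is easily put right and because over-age samples cannot be recovered afterwards.

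**What to change.** 1. In Section V, separate the two specimen types. State that fecal samples go to the core facility at least monthly and reach extraction within 60 days of collection, counting mailing time for the T4 samples. Buccal swabs can stay quarterly.
2. In the Gut Microbiome row of Table 1, change the specimen in the monthly transport sentence from buccal swab samples to fecal samples.
3. Use the collection date already on each label to record days from collection to extraction, and flag any sample over 60 days in the microbiome analysis.

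Cost: the wording changes, one derived data field, and some extra driving. Data collection runs from month 3 to month 15 in Table 2, which is 12 months. Monthly transport means about 12 trips against about 4 quarterly ones, so about 12 − 4 = 8 additional short car transports.
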